1.2 Secondary Aim

1.2.1 To further define the toxicities of the study arms in the treatment of translocation morphology RCC across all ages.

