Each cycle of therapy will be 4 weeks. Tumor disease evaluation will occur after Cycles 2, 4, 6, 9, 12, and then every 4 cycles thereafter, or at any time clinical progression is suspected. If pseudoprogression is suspected (until any degree of response is observed), disease evaluation must occur after every cycle ([Section 10.2.1](#)). Absent disease

progression or unacceptable toxicity, patients may continue on protocol therapy for up to 2 years duration or completion of 26 cycles, whichever comes first. Disease evaluations (including imaging) will continue during follow-up according to the schedule outlined in [Section 7.2](#).

For patients who progress on Arm C prior to Cycle 22, cross-over to Arm A is permitted. Patients should resume Arm A therapy as soon as PD is identified. Nivolumab should continue uninterrupted according to the previously established schedule for that patient (either every 2 or 4 weeks). Axitinib should be added as soon as it becomes available from NCI and the patient has recovered from any relevant toxicity. Subsequent disease evaluations should occur as above timed from the first cycle of combination therapy. The first cycle of combination therapy after cross-over will be defined as the cycle for which > 14 days of axitinib is given, with Day 1 of Cycle 1 after cross-over defined as the day of first nivolumab dose during that cycle after axitinib is started or on the day axitinib is started if given concurrently. **NOTE:** The total protocol therapy received on AREN1721 (whether delivered on Arm A, Arm C, or Arm C+A) is not to exceed 26 cycles or 2 years, whichever comes first.

NOTE:

- Patients who have not had cytoreductive nephrectomy prior to trial enrollment but who elect to have cytoreductive nephrectomy during therapy may remain on protocol therapy.
- Cytoreductive therapy is not permitted in the first 12 weeks after starting protocol therapy.
- Axitinib must be held for 7 days before and after surgery. See [Section 13.1.2](#) for more details.

For COG Supportive Care Guidelines see:

<https://childrensoncologygroup.org/index.php/cog-supportive-care-guidelines>.

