9.0 STATISTICAL CONSIDERATIONS

9.1 Sample Size and Study Duration

As of Amendment 5A, which now allows crossover upon progression from the nivolumab arm to the nivolumab + axitinib arm, we expect enrollment of approximately 2 patients per month. This is derived from tRCC prevalence, access to treatment centers, and enrollment patterns to date, which should be aided by the crossover.

To reduce the overall sample size from the prior design, we have maintained the same overall study design but changed two design parameters: 1-sided alpha will be increased from 0.05 to 0.15, and the targeted hazard ratio will be reduced from $HR = 0.50$ to $HR = 0.40$. With these changes, 22 PFS events will be required to address the primary objective comparing Arms A and C at the time of final analysis (see [Section 9.2](#)). Allowing that approximately 25% of eligible and evaluable patients may not have experienced a PFS event by the time of the final analysis, the target accrual on this study is 28 patients. To account for an additional estimated 5% of patients who might be found to be ineligible for the study or inevaluable for the primary endpoint at the time of or following study enrollment (e.g., due to randomization to Arm B, no central path review performed, or having central path review confirming a diagnosis other than tRCC), the ceiling accrual will be set to 40 patients, including those patients already enrolled.

If the study accrues to the target accrual without interim stopping for futility, the additional time required to enroll up to this maximum once re-opening under Amendment 5A is estimated to be 14 months. As before, all eligible patients will be followed for 5 years after randomization, and the final analysis will be conducted once the target number of PFS events needed for the final analysis has been reached, or after 2 years of follow-up is obtained for the last patient enrolled, whichever occurs first.

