9.3 Methods of Analysis

Primary Endpoint Analyses

The primary endpoint, progression-free survival, is formally defined in [Section 9.4](#) below. Due to the small size of this trial and the need to preserve alpha-spending for the final analysis, there will be no formal interim analyses of PFS for early efficacy, though this trial will be periodically reviewed by the COG DSMC.

Prospective formal interim analyses for futility will be performed once 50% (11) of the 22 targeted PFS events have been observed. The trial will stop early for futility if, given the data observed to date, the observed hazard ratio for PFS is greater than 1.00, suggesting a trend toward worse outcomes for Arm A (nivolumab + axitinib) compared to Arm C (nivolumab alone).

The final PFS analysis will be performed based on the first quarterly data freeze where at least one of the following criteria are met: (1) a minimum of 2 years of follow-up has been obtained for each patient still “at risk” for a PFS event or (2) when at least 22 PFS events needed for a fully powered final analysis have been confirmed. At this time, a stratified, one-sided log-rank test (using the stratification factors at randomization, age and prior therapy, if stratum-specific sample sizes allow) will be performed to compare treatment arms with alpha = 0.15. A stratified Cox proportional hazards model will also be fit to evaluate the final hazard ratio between the treatment arms (stratification as numbers allow); this will be reported with a 70% confidence interval (to align with the overall alpha level of the primary log-rank test).

While post-progression outcomes on combination therapy among patients who receive crossover upon first progression on the nivolumab-only arm (Arm C) will not be counted toward the primary endpoint analyses, their post-progression experience, including time from first progression to second progression or death (second PFS) will be summarized descriptively.

Secondary Endpoint Analyses

Secondary endpoints OS and ORR (defined in [Section 9.4](#) below) as well as all Grade 3 non-hematologic adverse events and all Grade 4 and higher adverse events will be monitored for data cleanliness and routine reporting as well as formally compared at the time of the final analysis for the primary endpoint, as described below. For ORR and OS below, stratifications factors again may be collapsed and/or omitted depending on the final counts.

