ORR: A logistic regression model for overall response, stratified by the stratification factors used at randomization (age and prior therapy) will be fit, including treatment arm as a key covariate. From this model, the odds ratio for treatment arm will be reported with a 70% confidence interval. The ORR observed within each treatment arm will also be reported.

OS: A stratified, one-sided log-rank test (using the stratification factors at randomization, age and prior therapy) will be performed to compare treatment arms with alpha = 0.15. Cox proportional hazards models will also be fit to evaluate the final hazard ratio between the treatment arms, with exploratory modeling taking into account the potential influence of other factors (e.g., baseline disease burden, upfront vs. delayed nephrectomy). From these models, the hazard ratio for treatment assignment will be reported with a 70% confidence interval (to align with the overall alpha level of the primary log-rank test).

AEs: All Grade 3 or higher non-hematologic toxicities and all Grade 4-5 adverse events occurring during protocol therapy or within 100 days of treatment discontinuation, including crossover for patients who receive crossover combination therapy, will be analyzed. The rates of these events will be reported separately by treatment arm (including crossover as a “3rd” arm for this purpose), and both by individual AE and class of AE (e.g., hematologic). Given that some AEs may be rare, Fisher Exact tests will be used to test for statistical significance among any apparent differences by treatment arm.

Exploratory Analyses

Exploratory Aim 1.3.1: To characterize tRCC clinical behavior across all age groups.
We will list and summarize the frequency of site(s) of disease at presentation (including extent of lymph node involvement), site(s) of relapse, surgical practices on protocol therapy, and radiotherapy practices on protocol therapy. We will also summarize the overall response rate (ORR) submitted by the enrolling institution.

Exploratory Aim 1.3.2: To evaluate type of antitumor immune response and stability of T cell activation before and after treatment with immunotherapy or antiangiogenic therapy.

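### The formal adverse event comparison is set at the PFS cut, when the defined on-therapy-plus-100-days window is still open for a material minority of patients, and no updated analysis is scheduled.

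*Combined protocol and SAP*

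**What the plan says.** Section 1.2 lists a single secondary aim: "To further define the toxicities of the study arms in the treatment of translocation morphology RCC across all ages".

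Section 9.3 (Secondary Endpoint Analyses) says that OS, ORR and the selected AEs are monitored for "routine reporting as well as formally compared at the time of the final analysis for the primary endpoint". That analysis takes place at the first quarterly data freeze at which one of two triggers is met: "when at least 22 PFS events needed for a fully powered final analysis have been confirmed", or "a minimum of 2 years of follow-up has been obtained for each patient still" at risk of an event. Section 9.1 has the same rule: "the final analysis will be conducted once the target number of PFS events needed for the final analysis has been reached", or 2 years after the last enrolment if that comes first.

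The AE paragraph of Section 9.3 covers Grade 3 or higher non-hematologic and all Grade 4-5 events "occurring during protocol therapy or within 100 days of treatment discontinuation". It includes cross-over treatment and reports it as a third group. Under Section 4.1, "patients may continue on protocol therapy for up to 2 years duration or completion of 26 cycles", whichever comes first, and that cap also covers therapy received after cross-over.

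Patients are followed for 5 years (Section 9.1), but no AE analysis is scheduled after the PFS analysis. No AE analysis time is given if the trial stops at the 11-event futility look.

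**The concern.** The timing and the scope in Section 9.3 do not fit together. At the PFS cut the defined window is unfinished for patients who are still event-free on treatment, for those who stopped within the previous 100 days, and for cross-over patients still on the combination. A table labelled as covering therapy plus 100 days would in fact cover different fractions of that window for different patients.

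The truncation need not be equal across groups. If axitinib delays progression, Arm A patients stay on drug longer and more of them are cut off. Cross-over exposure starts latest, although Section 2.6 wants it to inform tolerance. Section 5.3 notes that nivolumab events can appear several months after the last dose, and such events are the most exposed to an early cut.

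**Working it through.** **1. Document figures alone.**
- Longest window: 26 cycles × 28 days + 100 days = 828 days, about 27 months.
- Projected final analysis (Section 9.2 table): 17, 21 and 23 months after reopening for HR 1.0, 0.5 and 0.4.
- Since 23 < 27, at the average cut no patient enrolled after reopening can have completed full-length therapy plus 100 days.
- Patients at reopening, inferred from the table at 2 per month: 24 − 2 × 9 = 6 (HR 1.0) and 26 − 2 × 10 = 6 (HR 0.4). About 22 of the 28 therefore enter afterwards, and accrual ends near month (28 − 6)/2 = 11. Section 9.1 states 14 months to the maximum, which would leave the last patients less follow-up.
- Event-free at the cut: 28 − 22 = 6, or 21% (Section 9.1 allows about 25%). Those enrolled after reopening have open windows unless they stopped treatment more than 100 days earlier. Recent progressors and cross-over patients still on therapy add to them.

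**2. Reproducing the plan's design.** The control curve is in a figure that is not shown, so its hazard was calibrated to the stated durations (median 7 months for 9 months, then 4 months). The simulation used 20,000 trials, the HR > 1.00 futility rule at 11 events, and an unstratified log-rank test at 22 events.

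| | HR 1.0 | HR 0.5 | HR 0.4 |
|---|---|---|---|
| Final analysis, months: plan / reproduced | 17 / 17.1 | 21 / 20.8 | 23 / 22.5 |
| Early futility: plan / reproduced | 50% / 50% | 15% / 14% | 8% / 8% |
| Efficacy: plan / reproduced | 14% / 14% | 66% / 67% | 80% / 82% |

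The 2-year trigger fires first in under 1% of simulated trials. Median follow-up of the last patient at the cut is 7, 10 and 12 months.

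**3. Share of the 28 with an open window.** Cross-over uptake, second PFS, deaths and discontinuation are assumptions, because the documents give none.

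| Assumptions | HR 1.0 | HR 0.5 | HR 0.4 |
|---|---|---|---|
| No cross-over, no early stops, cut at event 22 | 38% | 34% | 31% |
| Same, at the quarterly freeze | 32% | 29% | 27% |
| 50% cross-over, second PFS median 4 months, 10% of events deaths, cut at event 22 | 39% | 35% | 32% |
| Same, at the freeze | 32% | 30% | 28% |
| 80% cross-over, second PFS median 8 months | 44% | 41% | 38% |
| 50% cross-over case plus 24% per year toxicity stops, at the freeze | 26% | 22% | 20% |

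The central range is about 20-44%. A pessimistic case (40% per year discontinuation, 20% of events deaths, short post-progression survival, quarterly freeze) gives 13-19%. Together this is roughly 15-45%. A longer control PFS could bring the share under 10%, but would contradict the stated 17-23 months.

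**4. By arm.** At HR 0.4, at the freeze and without cross-over, 39% of Arm A and 14% of Arm C windows are open. With 50% cross-over counted in Arm C the figures are 37% and 18%. At HR 1.0 with 50% cross-over they are 31% and 34%, so the excess in Arm A appears only if axitinib works.

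**5. Denominator.** Section 10.2.2.1 makes every treated patient evaluable for toxicity, and the enrolment ceiling is 40. If, for illustration, 6 further treated patients had closed windows, 20-44% of 28 (5.6 to 12.3 patients) becomes 5.6/34 to 12.3/34, or 16-36%.

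**6. Size of the undercount.** A similar simulation (80% cross-over, 0-24% toxicity stops in Arm A) with an assumed constant first-event hazard of 2-5% per month understates the crude rate by 2-5 points in Arm A and 1-11 points in about 9-10 cross-over patients. In patients: 0.02 × 14 = 0.3 to 0.05 × 14 = 0.7 in Arm A, and 0.01 × 9 = 0.1 to 0.11 × 10 = 1.1 in cross-over.

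**The case against.** Four points weigh against the concern.

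- **Scope has no cut-off.** A reader might infer that toxicity after the PFS cut is excluded from every planned analysis. The documents do not say that. The AE paragraph of Section 9.3 sets no data cut-off and says that events in the whole window will be analysed; only the formal comparison is tied to the PFS analysis. What stands is that the two statements need reconciling, because no time is set at which the full scope could be met.
- **The effect is small.** Under one patient in 14 is well inside sampling error: an observed 5/14 has an exact 95% interval of 13-65%. The assumed constant hazard also matters. Section 5.2.5.4 places the onset of hypertension in children mainly in Cycle 1, and early-onset events lose little to truncation. This stands, and it limits the weight of the point.
- **Safety surveillance continues.** DLT monitoring (Section 9.5), quarterly CDUS reports (12.1), DSMC review (12.2) and 100-day reporting of immune-related events (11.9.3, 11.10) are not tied to the PFS cut. They protect patients, but they are not a by-arm analysis of the secondary aim.
- **Later data are not automatic.** The follow-up list in Section 7.2 covers examination, laboratory tests and imaging. AE data come through Section 11, where the 100-day extension concerns nivolumab and immune-related events. An update therefore depends on Section 11 reporting, not on the 5-year follow-up as such.

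**Conclusion.** The point holds as a worthwhile, inexpensive improvement. From the text alone, the stated time of the AE comparison cannot accommodate the stated AE window, no later AE analysis is scheduled, and none is timed after a futility stop, which has a 50% chance under HR 1.0.

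The share of open windows, roughly 15-45% of the 28 PFS-evaluable patients, is a modelled figure. It rests on a control curve calibrated to the Section 9.2 durations and on assumed cross-over, second PFS and discontinuation, and it is smaller among all treated patients if the others' windows have closed. Quoting a single share as fact, or claiming that the between-arm toxicity comparison is seriously biased, would go beyond the documents. The direction is plausible: under-ascertainment, greater in Arm A than in first-line Arm C if axitinib works, with cross-over exposure starting latest. The absolute undercount is about one patient or less per group, on event hazards that the documents do not supply.

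**What to change.** In Section 9.3:

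1. Keep the AE comparison at the final PFS analysis, and state with it the data cut and, by arm and for cross-over, how many patients still have an open window.
2. Add an updated AE analysis (rates by arm and for cross-over, and the comparison) in all treated patients, at the first data freeze after every treated patient has ended protocol therapy and completed 100 days.
3. Apply the same rule if the trial stops for futility.

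**Cost.** One more table run, and a later complete toxicity result. The latest date is about 11 + 24 + 3.3 = 38 months after reopening, which is 38 − 23 = 15 to 38 − 17 = 21 months after the projected PFS analysis. With the 14-month accrual of Section 9.1 it would be about 41 months, or 18 to 24 months later. Either date is inside the 5-year follow-up, and it comes sooner if patients stop therapy early. PFS timing, alpha and treatment are unchanged.

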9.4 Endpoints and Evaluability

The primary endpoint is progression-free survival (PFS), which is defined as the time from randomization to the earliest occurrence of disease progression (as defined by modified RECIST criteria for immunotherapy, described in [Section 10](#)) or death due to any cause among patients who initiated protocol treatment. Patients not experiencing a PFS event by the time of a prospectively-planned interim or final analysis will be right-censored at the time of their most recent response/progression evaluation. Following the intent-to-treat principle, all patients who are randomized and confirmed to have tRCC by central pathology review will be evaluable for PFS. Patients randomized to Arm B prior to Amendment 2A, and patients who have a central path review confirming a diagnosis other than tRCC, or who never receive central path review per protocol, will be considered inevaluable for the primary endpoint comparison but included in study descriptive statistics.

The overall response rate (ORR) will be defined as the rate of complete or partial responses (assessed by imaging) among patients who initiated protocol therapy and completed at least one subsequent imaging assessment. Patients who are randomized to Arms A or C and are confirmed to have tRCC by central pathology review will be evaluable for ORR.

Overall survival (OS) will be calculated as the time from randomization to death due to any cause, with surviving patients being right-censored at their length of follow-up at the time of analysis. Patients who are randomized to Arms A or C and are confirmed to have tRCC by central pathology review will be evaluable for OS.

Note: For calculations of both PFS and ORR, any lesions resected during protocol therapy for reasons other than progression (as noted by sites or documented upon central surgical review) will not contribute toward response/progression assessments. Response/progression assessments are scheduled to take place after Cycles 2, 4, 6, 9, 12, and then every 4 cycles thereafter, after every cycle following any suspected pseudoprogression until the total tumor burden subsequently diminishes, or at any time clinical progression is suspected. Once in follow-up, patients without a documented PFS event will be evaluated according to the schedule in [Section 7.2](#). ORR and OS will be analyzed as a part of exploratory aim 1.3.1.

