13.1.2 Cytoreductive Nephrectomy

Cytoreductive nephrectomy is not required for patient enrollment; however, we encourage cytoreductive nephrectomy when feasible. Level I evidence from the prior immune-modulatory era (cytokine era) for treating metastatic renal cell carcinoma demonstrated the survival benefit of cytoreductive nephrectomy.^{64, 65} While we await randomized-trial data about the impact of cytoreductive nephrectomy in the current era of targeted therapy for metastatic renal cell carcinoma, analyses of retrospective and administrative data suggest that it may be beneficial in select patients.^{66, 67} Therefore, when possible we would encourage cytoreductive nephrectomy prior to beginning protocol therapy. Per [Section 3.2.8.3](#), patients must be more than 7 days out from major surgery (which includes open or laparoscopic nephrectomy) for eligibility. For the purposes of this study cytoreductive nephrectomy may include radical or partial nephrectomy and may be achieved by either an open or laparoscopic approach. Additionally, delayed cytoreductive nephrectomy is permitted 12 weeks after starting protocol therapy, taking into account the need for holding axitinib before and after nephrectomy per [Section 13.1.8.3](#).

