13.1.8.2 Restrictions for Patients with Tumor Growth

Any surgical tumor resection performed for lesions that are increasing in size (any increase in size based on radiology) will result in removal from protocol therapy.

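### The exploratory OS Cox models name on-study (delayed) nephrectomy as a covariate, and the plan does not say that the reported treatment hazard ratio comes from a model without it

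*Combined protocol and SAP*

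**What the plan says.** Section 9.3 (OS paragraph) makes a stratified one-sided log-rank test the formal comparison; it "will be performed to compare treatment arms with alpha = 0.15" and uses only the randomization factors, age and prior therapy. Cox models are fitted as well, with "exploratory modeling taking into account the potential influence of other factors (e.g., baseline disease burden, upfront vs. delayed nephrectomy" among the examples. The next sentence reads: "From these models, the hazard ratio for treatment assignment will be reported with a 70% confidence interval". It does not say whether this means the main Cox model, the exploratory ones, or both.

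Section 9.4 sets the time origin: "Overall survival (OS) will be calculated as the time from randomization to death due to any cause".

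Section 13.1.2 supplies the meaning of the covariate. Upfront surgery comes before treatment: "when possible we would encourage cytoreductive nephrectomy prior to beginning protocol therapy". The other level is on-study surgery: "delayed cytoreductive nephrectomy is permitted 12 weeks after starting protocol therapy". Section 13.1.8.1 removes from protocol therapy anyone whose tumor is resected earlier, and 13.1.8.2 adds: "Any surgical tumor resection performed for lesions that are increasing in size (any increase in size based on radiology) will result in removal from protocol". Section 4.2.5 asks that nephrectomy be reconsidered after 12 weeks where it was not done before enrollment, so delayed surgery is an expected event.

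No coding is given for the covariate: no time-dependent term, no landmark, no restriction to baseline status.

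**The concern.** The two example covariates differ in kind. Disease burden at baseline is fixed at randomization. Whether a patient ends up in the delayed group is settled months later, and depends on surviving to surgery and, on protocol, on the tumor not growing. With OS counted from randomization and delayed surgery entered as a fixed covariate, the death-free time before surgery is credited to surgery. That is immortal-time bias, with selection for good prognosis added to it.

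The two-level label also leaves no place for patients who never have a nephrectomy, including those who die before surgery is possible. Dropping them, or assigning them to a level, conditions on the outcome.

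What is at stake is the OS treatment HR if it is read from such a model, and any statement about nephrectomy drawn from its coefficient. The second matters because 2.1 presents the trial as a framework for tRCC treatment guidelines and 13.1.2 says randomized nephrectomy data are still awaited.

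**Working it through.** **The plan's own figures.** Section 9.3 gives no figure for the OS models. The stated power is for PFS. Freedman's formula at HR 0.40, one-sided alpha 0.15 and 80% power gives (1.036 + 0.842)² × (1.4/0.6)² = 3.527 × 5.444 = 19.2, or 20 events, against 22 planned. A two-look simulation with the futility stop at 11 of 22 events (Freedman drift) gives 81.0% power and 7.8% early futility at HR 0.4, 67.2% efficacy at HR 0.5, and 13.9% at HR 1.0. Section 9.2 states 80%, 8%, 66% and 14%. These figures reproduce, and this point does not touch them.

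**Deaths before delayed surgery is allowed.** Twelve weeks is 84/30.44 = 2.76 months. With exponential OS and median M months, the share dead by then is 1 − 2^(−2.76/M):
- M = 12: 15%
- M = 18: 10%
- M = 25: 7%

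The medians are assumptions. Section 2.2.2 gives 18.2 to 25.5 months for nivolumab in general RCC; there is no tRCC figure for nivolumab.

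**Simulation with surgery given no effect on OS.** Assumed inputs, not in the documents: the medians above; half of patients with the primary in place at baseline; 30 to 60% of these planned for delayed surgery, at 12 weeks plus 0 to 6 months; censoring at 24 to 42 months. Each scenario has 300,000 patients, so that bias rather than noise is seen. Coding is fixed in three groups (upfront, delayed, never).

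| Planned delayed surgery, Arm A vs Arm C | Treatment HR, unadjusted → adjusted |
|---|---|
| 40% vs 40% | 0.60 → 0.60; 1.00 → 1.00 |
| 60% vs 30% | 0.60 → 0.64–0.65; 1.00 → 1.07–1.08 |
| 30% vs 60% | 0.60 → about 0.56; 1.00 → about 0.93 |
| 60% vs 30%, surgery favoring good prognosis | 0.66 → 0.73; 1.00 → 1.11–1.12 |

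As ratios, the largest upward shift is 1.115/0.997 = 1.12. A typical one without prognostic selection is 0.647/0.604 = 1.07, and the reverse case gives 0.564/0.606 = 0.93.

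The coefficient for this ineffective surgery was 0.70–0.78 against upfront and 0.56–0.69 against never. With prognostic selection it was 0.56–0.61 and 0.40–0.46.

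**Second simulation, other assumptions.** Control median PFS 5 months; median post-progression survival 14 months; 40% upfront nephrectomy; delayed surgery at months 3–9 in 50–80% of the rest if progression-free; PFS HR 0.4; surgery with no effect. Here the arms differ in surgery only because more Arm A patients stay progression-free. The OS treatment HR moved from 0.57 to 0.59–0.63, about 4 to 10% (0.591/0.57 = 1.04; 0.629/0.57 = 1.10).

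**Dependence on coding.** If the model keeps only patients who had a nephrectomy (upfront or delayed), the treatment HR in the first simulation moves by no more than about 2% (for example 0.660 → 0.674). But this drops the never group: with 50% upfront and 14.5 to 20.4% delayed, that is 30 to 36% of patients.

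**Size against precision.** If all 28 target patients died, the 70% interval's half-width on the log scale would be 1.036 × 2/√28 = 0.39. The largest shift is ln(1.12) = 0.11, or 0.11/0.39 = 0.29 of it. With fewer deaths the fraction is smaller.

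**After the change.** Adjusting only for baseline nephrectomy left the treatment HR unshifted in every scenario. A time-dependent term brought the surgery coefficient back to about 1.00 without prognostic selection. With selection it still gave 0.71–0.78 and moved the treatment HR by up to about 3%.

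**The case against.** The adjustment is exploratory and introduced only as an example. The formal OS test uses randomized arms and baseline strata. Section 9.4 even says "ORR and OS will be analyzed as a part of exploratory aim 1.3.1", although 9.3 lists OS as a secondary endpoint to be formally compared. No coding is prescribed, so an analyst could handle delayed surgery correctly. Only a treatment HR is promised; no nephrectomy HR is planned. All of that stands, and it limits the point to one unclear sentence and one badly chosen example.

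A reader might go further and infer that immortal-time bias is built into the OS analysis and that part of the treatment effect is adjusted away. The documents do not support this:
- The coding is left open.
- No surgery rates by arm are given. The treatment HR moves only if the rates differ, and in either direction. The axitinib hold around surgery (13.1.8.3) falls on Arm A from the start and on Arm C only after crossover.
- Losing effect through mediation requires surgery to change survival, which both simulations set to zero.
- Twelve weeks is not an absolute survival requirement. A patient resected earlier leaves protocol therapy but stays in follow-up (8.1).

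The objection does not remove two facts: the named covariate is defined by an event after randomization, and the reporting sentence does not exclude models that contain it.

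**Conclusion.** The point holds as a correctable weakness in the exploratory OS modeling. The treatment HR can be shifted by roughly 4 to 12% if delayed nephrectomy is a fixed covariate and its rate differs by arm. The shift is toward the null or past it if Arm A has more delayed surgery, the opposite if Arm C has more, and absent if rates are equal. These sizes rest on assumed survival, uptake and timing and on three-group coding; neither simulation models crossover explicitly. The direction in this trial cannot be known from the documents. Any nephrectomy coefficient from such a model would be biased toward apparent benefit, but the plan does not promise one. With about 28 patients the shift is well inside the 70% interval, so this is a matter of sound specification and does not threaten the trial's conclusions on its primary endpoint.

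**What to change.** In 9.3, replace the upfront-versus-delayed example with nephrectomy before randomization (yes/no), and state that the reported OS treatment HR comes from Cox models using baseline covariates only.

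If on-study nephrectomy is explored, say that it will be a time-dependent covariate or analyzed from a landmark after week 12, that the result is descriptive of surgery, and that the treatment HR will not be taken from that model.

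The cost is a sentence or two. Section 10.2 already has sites record the date of, and reason for, each resection, so no new data collection is needed, and sample size and the formal tests stay as they are.
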